APPENDIX 6. Elotuzumab Administration Guidelines-Dose preparation, Reconstitution, Administration

Dose Preparation Instructions

After dilution in normal saline, elotuzumab infusion must be completed within 8 hours if kept at room temperature (25 °C). If a delay is anticipated after the dose has been diluted in normal saline, the prepared dose (properly identified) may be refrigerated at 2 °C to 8 °C for up to 24 hours. If stored under refrigerated conditions, the study drug solution should be equilibrated to room temperature (takes about 2 to 2.5 hours), and the container must be gently inverted to thoroughly mix the contents before administration. Do not use the accelerated warming method. If the storage time limit is exceeded, the prepared dose solution must be discarded and the reason documented by the pharmacist in the study drug accountability records.

Elotuzumab will be administered to each subject as an IV infusion, using an automated infusion pump set at the appropriate rate according to the dose administration section (see Administration Instruction section below). The dose of elotuzumab will be calculated using the subject's predose weight on Day 1 of each cycle, and then added to 0.9% saline for infusion.

Reconstitute elotuzumab lyophilized study drug, as described in steps 1 to 5.

Step 1: For a 400* mg vial of lyophilized elotuzumab, draw 17 mL of Sterile Water for Injection (SWFI), USP into a syringe equipped with an 18-gauge or smaller needle.

Step 2: Remove the flip-top from the elotuzumab vial.

Helsinki University Hospital Comprehensive Cancer Center Hematology
Clinical study protocol NMSG#24/15

Step 3: Place the vial upright on a flat surface and, using standard aseptic techniques, insert the syringe needle into the vial through the center of the rubber stopper and deliver 17 mL (into the 20-mL vial containing 400* mg elotuzumab) SWFI, USP, into the vial. Slowly remove the syringe needle out of the vial. A slight back pressure can be felt during the delivery of the SWFI into the vial, which is considered normal. The final volume of the reconstituted solution is approximately 17.6 mL, which includes the volume displaced by the solid cake. The concentration of elotuzumab in the reconstituted solution is approximately 25 mg/mL.

*400 mg is the label claim and how the vials are labeled. During the filling of the vials the manufacturer overfills the vials by 10% (40 mg) to ensure that the pharmacist can withdraw at least 400 mg. This is a standard practice for injectable products because it is not possible to withdraw the entire contents from the vial.

Step 4: Hold the vial upright and gently swirl the solution by rotating the vial to dissolve the lyophilized cake. Then gently invert the vial a few times in order to dissolve any powder that may be present on top of the vial or the stopper. Finally, hold the vial upright again and gently swirl the solution a few more times to dissolve any remaining particles. Avoid prolonged or vigorous agitation. DO NOT SHAKE.

Step 5: After the remaining solids are completely dissolved, allow the reconstituted solution to stand for 5 to 10 minutes.

It is acceptable to have small bubbles and/or foam around the edge of the vial. The reconstituted preparation results in a colorless to slightly yellow, clear to slightly opalescent solution containing approximately 25 mg/mL of elotuzumab.

Step 6: Once the reconstitution is completed, withdraw the calculated drug volume and further dilute with 230mL normal saline into an infusion bag. Elotuzumab solutions are compatible with polyvinyl chloride and

Helsinki University Hospital Comprehensive Cancer Center Hematology
Clinical study protocol NMSG#24/15

polyolefin bags. Examples of such bags include Viaflo, MacoPharma Easyflex N, Macoflex N, B Braun Excel, and Braun Ecobag.

Drug volume will be calculated based on subject weight: For example, a subject receiving 10 mg/kg elotuzumab who weighs 80 kg on Day 1 [predose] will require 800 mg of study drug for infusion. Withdraw 32 mL of elotuzumab (25 mg/mL) from 2 vials and add to an infusion bag already containing 230 mL saline, for a total of 262 mL to be infused.

Use a new sterile needle for withdrawing solution from each vial.

The same vial must not be used to prepare elotuzumab for more than one subject. Used elotuzumab vials will be stored until study drug accountability has been completed by the BMS designee, and destruction or return is authorized. Used vials do not need to be refrigerated.

Administration Instructions:

1. Administer through a low-protein-binding 0.22 - micrometer or smaller in-line filter (placed as proximal to the subject as is practical). Prime the infusion line with study drug before starting the infusion.
2. Set the IV pump to deliver the infusion at the rate of 0.5 mL per minute (including the drug in the line). The total time of infusion will vary depending upon the maximum tolerated mL/min infusion rate as discussed above.
3. Record every time the infusion is started and stopped and the reason why the start and stop occurred.
4. Monitor the IV setup and the subject's IV site frequently during infusion, checking for the correct infusion rate and IV site infiltration.
5. Ensure that the full volume of elotuzumab is infused.
6. After elotuzumab has been infused from the line, discontinue the infusion, disconnect the IV tubing, and dispose of materials appropriately according to the facility's standard procedure.

Helsinki University Hospital Comprehensive Cancer Center Hematology
 Clinical study protocol NMSG#24/15
 Appendix 7

Serious Adverse Event Report						1/1
Study name / code: KED NMSG#24/15						
EudraCT number: 2016-001176-13						
Study site:						
Principal investigator:						
Report type:		Initial 		Follow-up 		
I Reaction information						
SUBJECT NUMBER	DATE OF BIRTH (dd.mm.yyyy)	AGE (y)	SEX	ONSET DATE (dd.mm.yyyy)	END DATE (dd.mm.yyyy / ongoing)	CHECK ALL APPROPRIATE TO ADVERSE REACTION
						 Patient died
EVENT DESCRIPTION (including relevant tests / lab data)						 Life threatening
						 Involved or prolonged inpatient hospitalisation
						 Involved persistent or significant disability or incapacity
						 Congenital anomaly
OUTCOME OF SAE						 Other medically important condition
Resolved 	Resolved with sequela 	Ongoing 	Fatal 	Unknown / Lost to follow-up 		
II Suspect drug(s) information						
SUSPECT DRUG (include generic name)					Did reaction abate after stopping drug?	
					Yes 	No 
					NA 	
DAILY DOSE(S)					Did reaction reappear after reintroduction?	
ROUTE(S) OF ADMINISTRATION					Yes 	No 
INDICATION(S) FOR USE					NA 	
THERAPY DATES (dd.mm.yyyy)			THERAPY DURATION		Was the blinding code broken?	
from:		to:			Yes 	No 
				NA 		
III Concomitant medication and history						
CONCOMITANT DRUG(S) AND DATES OF ADMINISTRATION (excluding those used to treat reaction)				OTHER RELEVANT HISTORY (e.g. diagnostics, allergics, pregnancy with last month of period etc.)		
Causality			SUSAR (Suspected Unexpected Serious Adverse Reaction)			
Probable 	Possible 	Unlikely 	Yes 		No 	
Name of reporter and role in study _____ Date _____ Signature _____						

Helsinki University Hospital Comprehensive Cancer Center Hematology
Clinical study protocol NMSG#24/15

**Suspected Unexpected Serious
Adverse Reaction Report**

1(1)

Study name / code: KEd NMSG#24/15

EudraCT-number: 2016-001178-13

Study site:

Principal Investigator:

I Reaction information						
SUBJECT NUMBER	DATE OF BIRTH (dd.mm.yyyy)	AGE (y)	SEX	ONSET DATE (dd.mm.yyyy)	END DATE (dd.mm.yyyy / ongoing)	CHECK ALL APPROPRIATE TO ADVERSE REACTION
						 Patient died
EVENT DESCRIPTION (including relevant tests / lab data)						 Life threatening
						 Involved or prolonged inpatient hospitalisation
						 Involved persistence or significant disability or incapacity
						 Congenital anomaly
OUTCOME OF EVENT						 Other medically important condition
Resolved 	Resolved with sequela 	Ongoing 	Fatal 	Unknown / Lost to follow-up 		
II Suspect drug(s) information						
SUSPECT DRUG (include generic name and manufacturer)					Did reaction abate after stopping drug?	
					Yes 	No 
					NA 	
DAILY DOSE(S)					Did reaction reappear after reintroduction?	
ROUTE(S) OF ADMINISTRATION					Yes 	No 
INDICATION(S) FOR USE					NA 	
THERAPY DATES	from: (dd.mm.yyyy)	to: (dd.mm.yyyy)	THERAPY DURATION			
III Concomitant medication and history						
CONCOMITANT DRUG(S) AND DATES OF ADMINISTRATION (excluding those used to treat reaction)				OTHER RELEVANT HISTORY (e.g. diagnostics, allergies, pregnancy with last month of period etc.)		
Report type: Initial  Follow-up 						
Name of reporter and role in study			Date		Signature	

Version 1.11.2017

Helsinki University Hospital Comprehensive Cancer Center Hematology
Clinical study protocol NMSG#24/15

CIOMS FORM

SUSPECT ADVERSE REACTION REPORT										

I. REACTION INFORMATION

1. PATIENT INITIALS (first, last)	1a. COUNTRY	2. DATE OF BIRTH			2a. AGE	3. SEX	4-6 REACTION ONSET			8-12 CHECK ALL APPROPRIATE TO ADVERSE REACTION  PATIENT DIED  INVOLVED OR PROLONGED INPATIENT HOSPITALISATION  INVOLVED PERSISTENCE OR SIGNIFICANT DISABILITY OR INCAPACITY  LIFE THREATENING
		Day	Month	Year	Years		Day	Month	Year	
7 + 13 DESCRIBE REACTION(S) (including relevant tests/lab data)										

II. SUSPECT DRUG(S) INFORMATION

14. SUSPECT DRUG(S) (include generic name)		20. DID REACTION ABATE AFTER STOPPING DRUG?  YES  NO  NA
15. DAILY DOSE(S)	16. ROUTE(S) OF ADMINISTRATION	21. DID REACTION REAPPEAR AFTER REINTRODUCTION?  YES  NO  NA

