Across two randomized studies (CA204004, CA204009), elotuzumab combined with lenalidomide or bortezomib demonstrated compelling evidence of benefit as measured by clinically meaningful improvements in progression free survival, response rate, durability of response and trend in overall survival. The CA204004 and CA204009 trial demonstrate that elotuzumab 10 mg/kg combined with standard of care therapy results in a clinically meaningful median PFS of 19.4 and 9.7 months compared to significantly shorter PFS with Ld or Bd treatment, respectively. More importantly, a proportion of subjects experience a prolonged benefit as evidence by a 1 and 2-year PFS rate of 68%/48% for E-Ld and 1 year PFS rate of 39% for E-Bd. The improvement in ORR is bolstered by the median durability of 20.7 and 10.3 months for E-Ld and E-Bd, respectively. Finally, the preliminary trend in overall survival favoring elotuzumab treatment was consistently observed with E-Ld with 1 and 2-year OS rates of 91%/74% and a 1 year OS of 85% with E-Bd.

Elotuzumab has an acceptable and manageable safety profile in relapsed or refractory MM subjects. Minimal incremental AEs were reported beyond those associated with lenalidomide or bortezomib therapy, particularly evidenced by exposure adjusted event rates. Infusion reactions are mitigated with a standard premedication regimen and infusions of 10 mg/kg of elotuzumab up to 5 mL/min appear safe and tolerable. Elotuzumab's safety profile supports its use in long-term treatment, young and elderly patient population and in those with normal or impaired renal function.

Elotuzumab presents a novel, specific treatment for MM that engages the innate immune system through natural killer cells to specifically kill myeloma cells. Elotuzumab demonstrates a favorable benefit-risk profile in MM patients who have received one or more prior therapies in combination with Ld or Bd, nearly all of whom ultimately relapse and die with existing therapies. These results clinically validate the novel immunotherapeutic strategy of targeting SLAMF7 in this lethal hematologic malignancy. The randomized trials, CA204004 and

Helsinki University Hospital Comprehensive Cancer Center Hematology
Clinical study protocol NMSG#24/15
CA204009, provide compelling evidence that elotuzumab provides long-lasting therapeutic outcomes and represents an important approach to treating MM.

Clinical pharmacodynamics of elotuzumab

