5.3 ELOTUZUMAB ADMINISTRATION

TABLE 10. Product information table – product description

Product description and dosage form	Potency	Primary packaging (volume)/label type	Appearance	Storage conditions (per label)
Elotuzumab powder for solution for infusion	300mg /vial or 400 mg/vial	20 ml vial /Open label	Sterile white to off-white, preservative-free, lyophilized cake	Store at 2°C –8°C Protect from light. Do not freeze or shake

Administration and handling of elotuzumab (See also Appendix 6)

The lyophilized elotuzumab drug product should be stored at 2°C to 8°C. Prior to administration the drug must be reconstituted with sterile water for injection, then further diluted in 0.9% sodium chloride normal saline. After the dose is diluted in normal saline, the elotuzumab infusion must be administered within 8 hours if stored at room temperature. If a delay is anticipated, the prepared dose may be refrigerated at 2°C to 8°C for up to 24 hours. If stored under refrigerated conditions, the prepared study drug solution should be equilibrated to room temperature (this takes 2-2.5 hours) and the container must be gently inverted to mix well before administration. Do not use the accelerated warming methods. If administration is delayed beyond the specified time, the prepared dose solution must be discarded, and the reason documented. The dose of elotuzumab to be given to a study patient will be calculated by multiplying the patient's weight (kg) by 10 mg/kg.

Premedication before elotuzumab

Dexamethasone

On weeks without elotuzumab, administer the weekly dose of 40 mg dexamethasone orally on day 1, 8, 15, and 22 (-1 to +3 days). At the investigator's discretion, the oral dexamethasone may be given as a split dose over 2 consecutive days each week.

On weeks of elotuzumab infusion, split the weekly dose of dexamethasone between oral and IV administration as indicated below under "Premedication Before Elotuzumab"

At the discretion of the investigator, the oral dexamethasone component may be given as a split dose 12 – 24 hours and 3 hours prior to elotuzumab

Premedication before elotuzumab

1. Dexamethasone 28 mg po (between 3 - 24 hours prior to the start of elotuzumab infusion or as a split dose 12 – 24 hours and 3 hours prior to elotuzumab) and
2. Dexamethasone 12 mg IV (on the day of elotuzumab infusion 45-90 minutes prior to the start of infusion).

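### Appendix 6 gives one elotuzumab pump rate, which overruns the protocol's 8-hour limit if it is held, and the rule for raising it is missing

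*Protocol*

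**What the plan says.** All the operative text is in the Protocol.

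- **Rate.** The dose preparation part of Appendix 6 sends the reader forward to the Administration Instructions for the pump rate. Step 2 there reads: "Set the IV pump to deliver the infusion at the rate of 0.5 mL per minute (including the drug in the line"). It continues: "The total time of infusion will vary depending upon the maximum tolerated mL/min infusion rate as discussed above".
- **Volume.** The worked example in Appendix 6 has "a subject receiving 10 mg/kg elotuzumab who weighs 80 kg on Day 1 [predose] will require 800 mg of study drug for infusion". At 25 mg/mL this is 32 mL, added to 230 mL of saline, "for a total of 262 mL to be infused". Step 5 asks for the whole volume to be given.
- **Time.** Appendix 6 says that after dilution the "elotuzumab infusion must be completed within 8 hours if kept at room temperature". Section 5.3 has a similar limit in different words: "the elotuzumab infusion must be administered within 8 hours if stored at room temperature".
- **Other mention of a rate.** Section 1.4.1, summarising earlier elotuzumab studies, says that "infusions of 10 mg/kg of elotuzumab up to 5 mL/min appear safe and tolerable".

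**The concern.** Rate, volume and time limit are three figures in one appendix, and any two of them determine the third. Taken at face value they do not fit together, and the sentence that might resolve the mismatch refers to text that is not there. Someone preparing an infusion is sent forward to the Administration Instructions for the rate, finds 0.5 mL/min, and is then sent back to a discussion that neither Appendix 6 nor section 5.3 contains.

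This matters in a trial whose stated objective is safety and feasibility. Sections 1.4.1 and 1.4.1.1 describe infusion-related events as the key elotuzumab-related events. Section 10.1 says there is no prior experience with this combination. Elotuzumab is infused two or three times in every cycle, at several centres. Without a common rate rule, differences in infusion reactions between centres or cycles could partly reflect how fast the drug was run.

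**Working it through.** **Inputs (Protocol)**

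- Dose 10 mg/kg; concentration 25 mg/mL; saline 230 mL (Appendix 6, reconstitution step 6)
- Rate 0.5 mL/min (Appendix 6, Administration Instructions, step 2)
- Limit 8 h = 480 min, for a dose kept at room temperature after dilution (Appendix 6, Dose Preparation Instructions)

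**1. Reproduce the protocol's own volume**

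Volume = weight × 10 / 25 + 230 mL. For 80 kg: 800 mg / 25 mg/mL = 32 mL, and 32 + 230 = 262 mL. This agrees with the appendix.

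**2. Duration if the rate is held at 0.5 mL/min**

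Duration = volume / rate = 262 / 0.5 = 524 min = 8.73 h. The excess is 524 − 480 = 44 min, with the pump assumed to start at the moment of dilution.

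**3. Is the 80 kg example unusual?**

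| Weight (kg) | Volume (mL) | Time at 0.5 mL/min (h) |
|---|---|---|
| 40 | 246 | 8.20 |
| 60 | 254 | 8.47 |
| 80 | 262 | 8.73 |
| 100 | 270 | 9.00 |

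In 480 min the pump delivers 0.5 × 480 = 240 mL. The saline takes up 230 mL of that (460 min), which leaves 10 mL of drug, or 250 mg. At 10 mg/kg this is the dose for 25 kg. The trial enrols adults, so at a constant 0.5 mL/min the limit would in practice never be met.

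**4. How large a change of rate removes the overrun?**

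For the 262 mL example, 262 / 480 = 0.546 mL/min averaged over the infusion would just meet the limit. At the background figure of 5 mL/min the same volume would take 262 / 5 = 52.4 min. Both figures are given for scale only and neither is a proposal.

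**5. Look for the rule that step 2 refers to**

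- Appendix 6 before step 2 covers storage, reconstitution, dilution, the example volume and the in-line filter. It gives no rate.
- Section 5.3 covers storage, dose calculation and premedication, including changes to premedication after a previous infusion reaction. It gives no rate.
- Section 1.4.1 gives the 5 mL/min figure as a finding from earlier studies. It has no steps, intervals or conditions for this trial.

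**The case against.** The strongest reply is that step 2 should be read as a whole. Its second sentence says that total time varies with the maximum tolerated rate. At a fixed 0.5 mL/min, total time would depend on volume alone, so the sentence makes sense only if the rate can rise. On that reading 0.5 mL/min is where the pump is first set, and the working above shows that a small increase in the average rate brings the 80 kg example within 8 hours. This stands: the overrun is conditional on the rate staying at 0.5 mL/min. A reader might infer that every adult infusion breaks the limit when the protocol is followed as written, and the documents do not support that.

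Two other stronger readings also fail.

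- **Stop and discard.** A reader might infer that an infusion passing 8 hours must be stopped and thrown away, in conflict with the full-volume instruction in step 5. The discard rules in section 5.3 and Appendix 6 concern a prepared dose that is stored too long or whose administration is delayed. Neither addresses an infusion already running.
- **A tenfold contradiction.** A reader might set 0.5 against 5 mL/min as conflicting instructions. An initial setting and an upper bound seen in earlier studies can both be true.

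It is also fair to say that no stated figure is miscalculated. The response rate endpoint, the sample size and the grade 3 or higher non-haematological threshold do not depend on this point.

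The reply does not supply the missing rule. Reading 0.5 mL/min as a starting rate means that the protocol should say when the rate rises, by how much and to what ceiling, and it does not. The text of step 2 is unbroken, with no redaction or missing figure nearby, and an infusion rate is not something a statistical analysis plan would supply.

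**Conclusion.** The point holds as an internal inconsistency with two branches, and the instruction is incomplete on both.

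- **Rate held at 0.5 mL/min:** the protocol's own example runs 44 min past its own limit (524 against 480 min), and every patient above 25 kg exceeds it. This assumes that the bag is kept at room temperature, that the infusion starts at the moment of dilution and that it runs without interruption. Handling time or pauses would lengthen it.
- **0.5 mL/min as a starting rate only:** no breach follows, but the rule for raising the rate is in neither Appendix 6 nor section 5.3, and the background figure in section 1.4.1 cannot serve as one.

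A secondary mismatch adds to this. Appendix 6 requires the infusion to be completed within 8 hours, whereas section 5.3 says administered, which could be read as started.

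The consequence is for uniform administration and for interpreting infusion-reaction data, not for the efficacy analysis. The front matter removed before review is an unlikely place for a rate rule, but it could not be checked.

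**What to change.** Reconcile section 1.4.1, section 5.3 and Appendix 6 (Dose Preparation Instructions, the worked example and Administration Instructions step 2). Insert the rate text that step 2 refers to, or correct the cross-reference if that text is elsewhere. State whether 0.5 mL/min is a starting or a constant rate, and use one wording of the 8-hour limit in both places. Then check the result against the 262 mL example, so that rate, volume and time limit agree. The drug supplier should confirm which figures apply. No rate, ceiling or time limit is proposed here.

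The cost is a correction to one appendix page, aligned wording in section 5.3, and a memo to sites. Design, endpoints and sample size are unaffected.

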17. INDICATION(S) FOR USE		
18. THERAPY DATES (from/to)		19. THERAPY DURATION

III. CONCOMITANT DRUG(S) AND HISTORY

22. CONCOMITANT DRUG(S) AND DATES OF ADMINISTRATION (exclude those used to treat reaction)
23. OTHER RELEVANT HISTORY (e.g. diagnostics, allergies, pregnancy with last month of period, etc.)

IV. MANUFACTURER INFORMATION

24a. NAME AND ADDRESS OF MANUFACTURER	
	24b. MFR CONTROL NO.
24c. DATE RECEIVED BY MANUFACTURER	24d. REPORT SOURCE  STUDY  LITERATURE  HEALTH PROFESSIONAL
DATE OF THIS REPORT	25a. REPORT TYPE  INITIAL  FOLLOWUP

